We propose a single blinded, randomised prospective trial to risk profile our AF patients according to their non-invasive assessment of peripheral or central blood pressure including aortic stiffness estimate. The impact of central blood pressure, on the atrial electrophysiological substrate and clinical outcomes will be analysed. In addition, the relationship between central high blood pressure and non-invasive indicators of end organ (cardiac, vascular, renal and retinal) injury will be explored.

Specific Aims

The specific aims of the project are:

- 1. To determine the prevalence of central high blood pressure and aortic stiffness amongst AF patients referred to Centre for Heart Rhythm Disorders (CHRD), University of Adelaide.
- 2. Prognostic impact of central high BP treatment to pre-defined targets as per age (Table-1) on clinical outcomes in AF patients categorised as pre-HTN or HTN during brachial blood pressure assessment with or without HTN induced end organ insult.
- 3. To assess the correlation between indices of central high blood pressure and endorgan damage including structural as well as electrophysiological changes of left atrium, LV diastolic dysfunction including LVH and HTN nephropathy.
- 4. To assess the role of central blood pressure indices including central blood pressure response to exercise and posture in risk profiling of arrhythmia patients over and above conventional brachial BP.
- 5. Defining AF as an index of end organ insult secondary to HTN.

B. BACKGROUND AND PRELIMINARY STUDIES:

Introduction

HTN poses a major risk in development of AF and premature cardiovascular events [1, 2, 3{Schnabel, 2009 #926, 11, 12]. However, definition of HTN is a moving target and "optimal" treatment goals are still not clear. Besides epidemiological studies advocate BP control of \leq 120/80 mmHg from vascular risk standpoint, no strong outcome benefits of achieving such BP goals were reported by primary prevention studies in patients with

HIGH IMPACT AF Study Protocol Version 3.1, November 2017

low risk of cardiovascular disease (CVD) [13-15]. Having said that, "SPRINT" strongly advocates aggressive BP control to improve outcomes in HTN patients with intermediate baseline risk of CVD (2%/ year) {Williamson, 2016 #931}, but guidelines are yet to incorporate lower BP treatment targets ($\leq 120/80$ mmHg) in population at high risk of CV events [14]. In addition, stress induced HTN including white coat HTN and blood pressure response to exercise [16] are not very well defined in terms of treatment and outcome in guidelines.

Traditionally, clinical blood pressure assessment is performed by a sphygmomanometer applied at the brachial artery, providing measures of peripheral systolic and diastolic blood pressure [18, 19]. However, population studies revealed that up to one fifth of the participants characterised as "normotensives" based on their brachial blood pressure could have central high blood pressure leading to aortic stiffness [8]. Central blood pressure appraisal quantifies the aortic pressure and pulsatile load an organ is exposed to and has additional predictive value over and above conventional brachial blood pressure assessment in cardiovascular outcomes [17].

Central Blood Pressure Evaluation - Non-invasive assessment

Historically, measurement of central blood pressure required central arterial catheterization for direct manometry. However, non-invasive assessment can be performed by echocardiography or a variety of cuff based devices using pressure or flow wave to calculate pulse wave velocity with central pressure indices [20]. The device based on principles of applanation tonometry or sphygmomanometer are routinely used to calculate PWV and the central arterial waveform[20].

Together, these clinical and experimental observations have led us to hypothesize a role for central blood pressure elevation in the pathophysiology and prognosis of AF. Through this low risk study, we will explore the role of central blood pressure and aortic stiffness assessment in risk profiling of our AF patients. In addition, we will demonstrate the impact of aggressive central blood pressure control on AF and cardiovascular outcomes.

C. STUDY POPULATION

PAF patients, fulfilling the inclusion criteria will be recruited from Centre for Heart Rhythm Disorders (CHRD), Royal Adelaide Hospital (RAH), University of Adelaide and Cardiovascular Centre, Norwood (Professor [name]'s rooms). The participants (125 in each arm), will be randomized to intervention or control arm during the recruitment phase over a study period of 24 months. Participants will be risk profiled according to their age (30-50, 50-70, > 70 yrs.) and baseline central blood pressure (pre-HTN, HTN with or without end organ insult) into three groups. The control group will have conventional risk stratification as per brachial BP.

The following inclusion and exclusion criteria will be applied:

Inclusion Criteria

- 1. Age 20-80 years
- 2. Persistent and Paroxysmal AF patients
- 3. Able and willing to provide written informed consent

Protocol for HIGH IMPACT- AF study

Centre For Heart Rhythm Disorders, Royal Adelaide Hospital, University of Adelaide

Exclusion Criteria

- 1. Age <20years
- 2. Contraindications to exercise stress test (EST)
- 3. Pregnancy
- 4. Active malignancy or severe illness
- 5. Active Inflammatory disorder
- 6. Severe Aortopathy
- 7. Advanced valvular heart disease including aortic insufficiency (AI)
- 8. Constrictive or restrictive cardiomyopathy
- 9. Contraindications to non-contrast CMR (*only in selected patients scheduled for* *PVI*)

Withdrawal Criteria

Participants may withdraw at any time from the study. Patient will be excluded from the study if she will become pregnant during follow up.

D. STUDY DESIGN, TIME LINE AND INTERVENTIONS

It is a single centre, single blinded, prospective, randomised control study to collect and compare data to risk stratify our AF patients according to their aortic stiffness severity and central or peripheral blood pressure. Participants will be randomised to intervention or control group.

Intervention group will have their anti-hypertensive therapy titrated as per central blood pressure targets (Table-1), while the control group will have their brachial blood pressure treated as per current treatment guidelines (BP \leq 140/90 mmHg if risk of CVD is \leq 1% per year or 130/80mmHg if CVD risk is \geq 2% per year [21].

In addition, participants will be categorised according to their age (20-50yrs, 50-70yrs and >70yrs) and blood pressure into pre-HTN or HTN with or without end organ damage.

Off note that the reported "normal range" of central blood pressure is estimated invasively while the participants are monitored in a controlled environment and under the effect of mild sedation. To prevent any harm to our study participants, we will take a holistic approach to risk stratify our patients while instigating treatment based on central or brachial pressures in order to avoid symptomatic hypotension along with drug side effects. The risk profiling will include age of the participants, aortic pulse wave velocity, baseline BP, degree of HTN induced end organ injury, BP response to exercise and central or brachial pressure indices including pulse pressure.

In case if patient has presenting BP characterised as grade II or higher HTN, a graduated approach will be adapted to lower the BP gradually by keeping an eye on the side effects of anti-HTN treatment.

CASP normal range						
Age (years)	Average (mmHg)	Minimum (mmHg)	Maximum (mmHg)			
20-30	101	90	112			
30-40	105	94	116			
40-50	108	97	119			
50-60	112	101	123			
60-70	115	104	126			
70-80	119	108	130			
80-90	122	111	133			

Table-1. Central Arterial Systolic Pressure (CASP) normal range as per age.

All AF patients will be assessed at baseline visits and at clinical follow-ups at RAH and Cardiovascular Centre, Norwood (Prof. [name]' rooms). Follow-up visits will be performed 3 monthly for the intervention group and six monthly for control as per treating electrophysiologist for 18-20 months (Tables 2 and 3). Participants will be risk stratified as per their central or brachial blood pressure indices into interventional and control group respectively.

The study will be approved by the ethics committee of RAH, University of Adelaide. Central blood pressure indices and carotid-femoral PWV analysis will be performed as per IMPULSE-AF validation study protocol. (CALHN Ethics and Research Committee Approval: R2010712, HREC Reference: HREC/16/RAH/269).

Table-2. Follow up and Investigations time line for Intervention Group (AFSS= AF symptom scale, CBP= central blood pressure, CPI= central pressure indices, EST= exercise stress test, PWV= pulse wave velocity, RFTs= Renal function test)								
0 months	3 months	6months	9months	12 months	15months	18-20 months		
Demographics and cardiovascular (CV) risk profiling	CPI and PWV including lying and standing CBP	CPI and PWV including lying and standing CBP	CPI and PWV including lying and standing CBP	CPI and PWV including lying and standing CBP	CPI and PWV including lying and standing CBP	CPI and PWV including lyin and standing CBP		
*CPI and PWV including lying and standing CBP (Sphygmocor)	AFSS, RFTS	AFSS, RFTS	AFSS, RFTs	AFSS, RFTs	AFSS, RFTs	AFSS, RFTs		
Echo, EST, Holter 4-7 days, AFSS, Retinal examination, Serum and urinary analysis.	Holter 4-7 days	Holter 4-7 days	Echo, EST, Holter 4-7 days, Serum and urine analysis	Holter 4-7 days, Retinal examination	Holter 4-7 days	Echo, EST, Holter 4-7 day Retinal examination, Serum and uri analysis		

Tables to illustrate follow up and intervention time lines for two groups

*Offer treatment as per central BP targets. (Table-1).

Additional electro-anatomical mapping to estimate scar burden along with CMRI will be offered to patients listed for AF ablation. The CMR will be repeated after 12 months to assess AAD in a year as per IMPULSE AF protocol (CALHN Ethics and Research Committee Approval R2010712, HREC Reference: HREC/16/RAH/269)

Table-3. Follow up and Investigations time line for Control Group (AFSS= AF symptom scale, BBP= Brachial blood pressure, CBP= central blood pressure, CPI= central pressure indices, EST= exercise stress test, PWV= pulse wave velocity, RFTs= Renal function test)							
0 months	6months	11-13 months	18-20 months				
Demographics and cardiovascular risk profiling	BBP treatment targets as per current guidelines	BBP treatment targets as per current guidelines	BBP treatment targets as per current guidelines				
CPI, PWV (Sphygmocor) Brachial blood pressure (BBP) including lying and standing assessment, Retinal examination	Review for standard CV risk factor modification including AF and anti HTN treatment	Review for standard CV risk factor modification including AF and anti HTN treatment	Review for standard CV risk factor modification including AF and anti HTN treatment				
Echo, EST, Holter 4-7 days, AFSS, Serum and urine analysis. Conventional cardiovascular risk factor (CVRF) management as per treating physician	Holter 4-7 days, AFSS, Conventional CVRF management as per treating physician	Echo, EST, Holter 4-7 days, AFSS, Retinal examination, Serum and urine analysis. CVRF management as per treating Physician	Echo, EST, Holter 4-7 days, AFSS, Retinal examination, Serum and urine analysis. CVRF management as per treating Physician				

Additional electro-anatomical mapping to estimate scar burden along with CMRI will be offered to patients listed for AF ablation. The CMR will be repeated after 12 months to assess AAD in a year as per IMPULSE AF protocol (CALHN Ethics and Research Committee Approval R2010712)

Following assessments are standard for AF care and will be offered to all (control and intervention) participants.

a) Baseline Assessment

At baseline, following assessment will be performed for all participants:

- Weight and height recorded to calculate BMI.
- Demographics and conventional cardiovascular risk factors profiling by recording fasting glucose, lipid profile, age, gender, smoking history, systolic, diastolic, and pulse pressure.
- Brachial and aortic blood pressure (BP) assessment in a supine position after a resting period of 10 min by a mercury sphygmomanometer. Sphygmocor device will be applied to the right forearm over brachial artery to determine the central blood pressure indices as described previously (IMPULSE-AF protocol). Brachial blood pressure will be assessed by recording phase I and V of Korotkoff sounds to determine the brachial systolic and diastolic BP, respectively.
- Conventional 12-lead resting electrocardiograms (ECG) will be recorded and interpreted according to the Minnesota code (Mc).

Protocol for HIGH IMPACT- AF study

Centre For Heart Rhythm Disorders, Royal Adelaide Hospital, University of Adelaide

- Exercise stress test as per Bruce Protocol to assess exercise capacity.
- Blood will be drawn following a 12-hour fast to determine plasma lipids, fasting glucose, hs CRP and renal function.
- Trans-thoracic Echo (TTE) will be performed to assess Biventricular systolic and diastolic function along with left atrial size.
- 4 to 7days Holter monitoring to evaluate AF recurrence and arrhythmia burden

b) Exercise Tolerance Assessment

Exercise tolerance assessment as a part of AF management will be determined by Bruce protocol with gradual increase in treadmill gradient and velocity every 3 mins to achieve maximal target heart rate as per age by the following formula [220-Age for males, 220-Age x0.8 for females]. Where necessary, the test will be tailored as per individual age and effort tolerance with a view to assess the maximum workload performance with in period of 8-12 minutes. An experience doctor or an exercise physiologist will supervise the test. Continuous monitoring of 12 leads ECG and blood pressure will be performed. Data will be recorded continuously and stored digitally for analysis later on by an experienced exercise physiologist. Central pulse wave morphology and velocity will be determined pre and post exercise (+5minutes) by Sphygmocor device.

c) Holter Recording

4- 7 days Holter recordings will be obtained to determine recurrence of AF along with its burden. Briefly, a 3-lead electrocardiogram is recorded continuously by way of five electrodes positioned on the upper torso. Upon completion of the recording period, data will be imported into MediLog Darwin analysis software and automatically analysed by using R-wave detection.

E. STUDY INTERVENTIONS IN ADDITION TO STANDARD OF CARE IN AF PATIENTS

a) Non-invasive central blood pressure assessment

Non-invasive evaluation of central blood pressure indices and carotid-femoral PWV analysis will be performed as per IMPULSE-AF validation study protocol (CALHN Ethics and Research Committee Approval: R2010712, HREC Reference: HREC/16/RAH/269)

Non-invasive central blood pressure assessment will be performed at baseline, and at follow-up using the SphygmoCor applanation tonometry device (Fig 1). Central blood pressure indices, including central systolic, diastolic and pulse pressures with augmentation index will be recorded. Carotid-femoral pulse wave velocity (PWV) will be performed by applanation tonometry as per IMPULSE AF study protocol. The test is painless and typically takes10-15 minutes. In control patients, central blood pressure measurement will be performed as a single clinical assessment during their first visit after randomisation.

b) Atrial Fibrillation Severity Scale (AFSS)

Atrial Fibrillation Severity Scale (AFSS) will be used to quantify AF symptomatic burden. The AFSS is a validated scale with range of 3.25 [single

episode with minimal symptoms lasting for minutes] to 30 [continuous highly symptomatic episode lasting for 48 hours]. The scale also includes AF event frequency (scored 1-10), duration (scored 1.25-10) and global episode severity (scored 1-10). In addition, the AFSS assesses symptom severity via an associated symptom-specific continuous subscale (range, 0 [no symptoms] to 35 [severe symptoms]).

c) Serum and Urine Analysis

Venous blood samples (10ml) will be drawn from an antecubital vein after 10 minutes of supine rest and within five minutes following peak exercise to analyse atrial natriuretic peptide, serum markers of endothelial function (asymmetric dimethyl arginine, nitrate/nitrite), coagulation inflammation and fibrosis (C-reactive protein(CRP), tissue growth factor beta (TGF-B) and tumour necrosis factor (TNF)). Samples will be collected in appropriate tubes, centrifuged and plasma stored at -80°c. A preferably early morning urine sample will be collected to quantify albumin creatinine ratio (ACR).

- *d)* Recording of additional Electrophysiological (EP) parameters during AF ablation: Some of the study AF patients will be scheduled for pulmonary vein isolation (AF ablation) on clinical grounds at the Royal Adelaide Hospital. Conventionally, electro-anatomic mapping of the left atrium is performed by using the 3D mapping system during AF ablation. The following additional electrophysiological parameters will be recorded from the ablation catheter for these patients to characterise electro-anatomical atrial remodelling: effective refractory period, linear catheter conduction time, conduction velocity, proportion of fractionated electrograms, and bipolar voltage from the electroanatomic mapping system. This will add an extra 15mins to the procedure time without any additional requirements.
- *Non-contrast cardiac MRI (CMR) assessment of aortic distensibility.* In sub-group of 20-30 patients, scheduled for PVI (AF ablation) a non-contrast CMR will be performed to assess aortic distensibility (AAD) as per IMPULSE AF study Protocol (CALHN Ethics and Research Committee Approval: R2010712, HREC Reference: HREC/16/RAH/269). A repeat CMR will be performed to appraise (AAD) in a year's time.

f) Retinal photography and analysis

Retinal photographs will be acquired from AF patients at baseline and during their follow up appointments yearly. Retinal vascular calibre will be measured from photographs using a validated computer program[22]. Retinal arteriolar and retinal venular calibre equivalents will be measured, and correlated with changes in central or peripheral blood pressures[22]. The acquisition of retinal image takes couple of minutes and it is a painless procedure that does not require any specific preparation.

[figure not shown]

Fig. 1. Sphygmocor applanation tonometry device (http://atcormedical.com/sphygmocor.html)

F. OUTCOMES OF THE STUDY

Primary outcomes to be evaluated include:

Association and Impact of central blood pressure control on AF outcomes (recurrence and AF burden).

Secondary Outcomes:

- Prevalence of central high blood pressure and aortic stiffness in AF patients with normal brachial BP.
- Association of brachial and central blood pressure indices including aortic stiffness to end organ insult and electro-anatomical remodeling of atria in AF patients.
- Correlating central blood pressure treatment target goals to proportionate decrease in events [Nephropathy (20% increase in ACR or 15-20% drop in estimated glomerular filtration rate (eGFR)), Left ventricular hypertrophy (LVH)/mass, LV diastolic dysfunction. Left atrial area and conduit vascular remodeling.
- Defining exaggerated BP response to exercise and postural change in our AF cohort and relating it with outcomes.
- > Number of anti-HTN required to achieve BP targets.
- Adverse events secondary to anti-HTN drugs including symptomatic postural BP drop of >20mmHg, acute kidney injury and electrolytes imbalance requiring hospitalization.

G. ETHICAL CONSIDERATIONS

Clinical Equipoise

The study is a low risk, single blinded randomised trial to evaluate the impact and treatment of central high blood pressure on AF and CV outcomes. Central high blood pressure will be estimated by validated cuff based device (Sphygmocor) non-invasively. Vascular remodelling secondary to HTN, leads to aortic stiffness, which is a modifiable risk factor. At present, it is known that various anti-hypertensive agents can have significantly different effects on central aortic pressures despite similar brachial blood pressure valuation [23]. Agents such as inhibitors of the renin-angiotensin system and amlodipine could be started in individuals with increased aortic stiffness. As such, the investigators regarding the conduct of this study identify no specific ethical concerns.

Informed Consent

All patient participants will undergo a formal process of informed consent prior to study participation. Patients will be blinded with regard to their randomised group and will be treated for peripheral or central high blood pressure accordingly.

Drugs

No additional pharmaceuticals will be administered for the study protocol, with the exception of anti-HTN to achieve treatment target goals re central or brachial blood pressure. Side effects of anti HTN medication will be recorded by conventional clinical approach of reviewing the symptoms, documentation of postural drop in BP and monitoring of renal function tests during follow up or as required clinically.

Specific Safety Consideration

No significant increase in radiation dose is anticipated for the acquisition of electrophysiological data for the study because we are going to use 3D mapping to position the catheters in atria. The non-invasive assessment of blood pressure is not associated with any known risk. Retinal photography does not require any mydriatics.

H. ANALYSIS AND REPORTING OF RESULTS

Sample size calculation

Assuming the recurrence risk is 40% for AF in control, we estimate 90 patients in each group would give us 80% power to detect the 20% difference between groups at 5% significance level. Anticipating dropout rate of 28% over the course of the study, we would like to recruit 126 patients in each group.

Statistical Analysis

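### The population is stated two ways, and recurrence has no starting point for a participant already in AF at baseline, which puts the planned 80% power at risk

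*Protocol*

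**What the plan says.** Protocol section C describes recruitment with "PAF patients, fulfilling the inclusion criteria will be recruited from Centre for Heart Rhythm Disorders (CHRD". The abbreviation PAF is never expanded; paroxysmal AF is its usual reading. Inclusion criterion 2 in the same section lists "Persistent and Paroxysmal AF patients". The aims, design and outcome sections speak of AF patients without naming a type.

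Section F gives the primary outcome as "Association and Impact of central blood pressure control on AF outcomes (recurrence and AF burden"). Section D(c) says how both components are observed: "4- 7 days Holter recordings will be obtained to determine recurrence of AF along with its burden". Under D(a), the Holter at entry, before any trial treatment, is already described as evaluating recurrence. Nowhere does the protocol require sinus rhythm, or a rhythm-restoring procedure, before recurrence starts to count.

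Section E(d) adds: "Some of the study AF patients will be scheduled for pulmonary vein isolation (AF ablation) on clinical grounds". The only groupings named for participants are age and blood pressure/end-organ status (sections C and D).

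Section H sizes the trial on recurrence alone: "Assuming the recurrence risk is 40% for AF in control", then "we estimate 90 patients in each group would give us 80% power" "to detect the 20% difference between groups".

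**The concern.** One inconsistent word would matter little by itself. It matters here because the two readings give different populations for the outcome on which the trial is sized. If persistent AF is admitted, some participants may be in AF at entry and remain in it. With no starting rhythm defined, such a person shows AF on the baseline Holter and on every later one, and counts as an event in both arms whatever the blood pressure treatment does. Each one raises both event rates and narrows the difference between them.

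Two baseline features, AF type and being listed for ablation, plausibly bear strongly on the rhythm outcome, and neither is named as a stratification factor. Stratified allocation has to be fixed before randomisation, so a later analysis plan cannot supply it.

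**Working it through.** **Inputs from the protocol (section H):** control recurrence 40%; difference 20%; 90 evaluable per group; 80% power; 5% significance. Two-sided testing is assumed because sidedness is not stated. The difference is read as absolute (40% against 20%), since a relative reading (40% against 32%) would need 564 per group.

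**Input not in the protocol:** the share q of participants in continuous AF throughout. It is assumed, and shown as a range.

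**Step 1: reproduce the plan.** With p̄ = (p1 + p2)/2 and d = p1 − p2,

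n = [1.96·√(2p̄(1−p̄)) + 0.842·√(p1(1−p1) + p2(1−p2))]² / d²

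= [1.96·√0.42 + 0.842·√0.40]² / 0.04, which gives 82 per group, or 91 with continuity correction. The stated 90 agrees with the corrected figure.

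Power at n per group = Φ{ [d − 1.96·√(2p̄(1−p̄)/n)] / √[(p1(1−p1) + p2(1−p2))/n] }.

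At n = 90: (0.20 − 0.134)/0.0667 = 0.99, so power is 83.9%. It is 79.5% with continuity correction and 80.2% for Fisher's exact test.

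**Step 2: continuous AF counted as recurrence.** The rates become p1 = q + (1−q)·0.40 and p2 = q + (1−q)·0.20. Power is for the uncorrected test.

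| Assumed q | Control vs intervention | Power, all 90 per arm counted | At risk per arm, 90(1−q) | Power, at-risk set only (40% vs 20%) |
|---|---|---|---|---|
| 0 | 40% vs 20% | 83.9% | 90 | 83.9% |
| 10% | 46% vs 28% | 70.9% | 81 | 79.9% |
| 20% | 52% vs 36% | 58.1% | 72 | 75.0% |
| 30% | 58% vs 44% | 46.7% | 63 | 69.2% |

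**Step 3: milder assumptions.**
- Persistent patients recur at 40% in both arms with no treatment effect: 74.7%, 63.5% and 51.5% at shares of 10%, 20% and 30%.
- Persistent patients have a control rate of 50-60%, a share of 30-50%, and the same 20-point benefit: 78.7-82.0%.
- The 40% and 20% already describe the mixed population: 83.9%.

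**Step 4: can 40% and 20% already cover the mix?** If a share q is positive in both arms, everyone else must go from (0.40−q)/(1−q) to (0.20−q)/(1−q). At q = 10% that is 33% to 11%. At q = 20% it is 25% to 0%. Above 20% it is impossible. So this reading protects the power only when few participants are in continuous AF.

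**Step 5: chance imbalance.** The 95% limit for the between-arm difference in q is 1.96·√(2q(1−q)/90): 13.4 points at q = 30% and 14.6 points at q = 50%. The gap in event rate between patient types is 60 points in control (100 − 40) and 80 on intervention (100 − 20). The resulting shift in the arm difference is about 8-11 points at q = 30% and 9-12 points at q = 50%.

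**The case against.** The strongest reply is that the sizing is sound and the slip trivial. The recruitment sentence defers to the inclusion criteria, criterion 2 is explicit, and the rest of the protocol speaks of AF in general. The 40% is attached to AF, not to paroxysmal AF, and the 90 per group reproduces. AF burden is already part of the primary outcome and can be measured in either type. All of this stands. It makes the wording conflict minor, but it does not say when recurrence begins for a participant in AF at entry.

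Three stronger readings are tempting, and the documents do not support them:

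- A reader might infer that recurrence has no meaning in persistent AF. The protocol does not say so, and a patient restored to sinus rhythm can recur. What is missing is the starting point.
- A reader might infer that the trial fails to deliver 80% power. That needs the share in continuous AF, its event rate and its treatment effect, and the protocol gives none of them. Step 3 includes cases where little or nothing is lost.
- A reader might infer that chance imbalance in AF type could equal the effect sought. Step 5 gives shifts of at most about 12 points against 20, and the standard error of the unadjusted comparison already allows for such variation. The documents give no figure from which to size an imbalance in ablation.

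It is also fair that randomisation is valid without stratification, and that model adjustment is commonly left to the SAP, which is not at hand. The case for stratifying is therefore precision and timing, not validity.

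**Conclusion.** The point holds in a limited form. It is certain from the text that the population is worded two ways (taking PAF as paroxysmal AF) and that the recurrence outcome has no at-risk definition for a participant in AF at baseline. The loss of power is conditional. With 10-30% in continuous AF throughout, counted as events in both arms, and the rest following 40% against 20%, power at 90 per arm is about 71% down to 47%. It stays at about 79-84% if persistent patients share the effect or the 40% already covers the mix, and the latter is arithmetically possible only when the continuous-AF share is small. The protocol does not secure the favourable case, so the 80% is at risk rather than lost. The change is worth making before randomisation starts.

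**What to change.** 1. Reconcile the PAF wording in section C with inclusion criterion 2.
2. Define recurrence in participants at risk: those not in continuous AF on the baseline ECG and Holter, both already collected. Word it so that a paroxysmal episode on the baseline Holter does not exclude anyone. Because the set is fixed by a baseline feature, the randomised comparison is preserved. Participants outside it whose sinus rhythm is restored later then contribute to burden only.
3. Keep all participants in the AF-burden outcome.
4. Stratify the allocation by AF type (paroxysmal or persistent) and by whether ablation is already listed at baseline, and adjust the primary comparison for the same two factors.
5. Restate the power for the number expected in the recurrence set, with the assumed share shown: about 80%, 75% or 69% if 10%, 20% or 30% are not at risk.

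The cost is protocol wording, two stratification factors in the allocation list, and a less favourable stated power. The restriction does not restore the planned power in full: at an assumed 30% share it gives about 69%, against 47% when continuous AF is counted as recurrence.

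### Pregnancy after randomisation ends the patient's whole study participation, so later Holter, symptom and adverse-event data are lost when stopping titration and unsuitable tests would be enough

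*Protocol*

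**What the plan says.** Section C, Withdrawal Criteria, has two sentences. The first covers the patient's own decision: "Participants may withdraw at any time from the study". The second is mandatory: "Patient will be excluded from the study if she will become pregnant during follow up". Elsewhere pregnancy appears only as an entry exclusion.

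The inclusion criteria in section C admit "Age 20-80 years", and Table 1 gives central systolic ranges for the decades from 20 to 50, with upper limits of 112, 116 and 119 mmHg.

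On drugs, section G (Drugs) says: "No additional pharmaceuticals will be administered for the study protocol, with the exception of anti-HTN to achieve treatment target goals". Section G (Clinical Equipoise) adds: "Agents such as inhibitors of the renin-angiotensin system and amlodipine could be started in individuals with increased aortic stiffness".

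On safety, section F lists among the secondary outcomes "Adverse events secondary to anti-HTN drugs including symptomatic postural BP drop", together with acute kidney injury and electrolyte disturbance. Section G (Drugs) describes how these are captured: "Side effects of anti HTN medication will be recorded by conventional clinical approach of reviewing the symptoms", with postural pressure and renal function also checked.

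On routine care, section D introduces a list that includes the Holter with: "Following assessments are standard for AF care and will be offered to all (control and intervention) participants".

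**The concern.** The pregnancy rule is wider than its reason. Pregnancy is a good reason to stop titrating to targets that were not set for pregnancy, to stop contraindicated drugs, and to omit tests such as the treadmill. It is no reason to stop a Holter, a symptom questionnaire or the recording of side effects.

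Two things are at stake. The first is safety. Drug adverse events are a secondary outcome, yet recording for the trial ends when a patient who may have been exposed to a study-directed antihypertensive becomes pregnant. The second is follow-up as randomised: a patient leaves because of an event after randomisation, whether or not she would be willing to stay. A SAP could not repair this, because it can define analysis sets but cannot recover data that the protocol stopped collecting.

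**Working it through.** **1. What could continue (Tables 2 and 3, follow-up visits only)**

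| Test | Intervention (6 visits) | Control (3 visits) |
|---|---|---|
| Holter | 6 | 3 |
| AFSS | 6 | 3 |
| Exercise stress test | 2 | 2 |

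Holter and AFSS are due at every follow-up visit in both arms, so keeping a pregnant patient in observation needs no new scheduled test.

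**2. How much data could be lost.** The protocol gives no pregnancy rate, sex mix or age distribution. Assume 0 to 3 pregnancies among 250 patients (125 per arm, section C), which is 0 to 3/250 = 1.2%.

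- Scheduled follow-up Holters: 125 × 6 + 125 × 3 = 1,125.
- Upper bound lost: 3 × 6 = 18, or 18/1,125 = 1.6%. This requires all three to be in the intervention arm and to conceive before the 3-month visit.

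**3. The protocol's own sample size (section H).** The inputs are control recurrence 40%, a difference of 20% read as 40% against 20%, 5% significance taken as two-sided, and 80% power.

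- Uncorrected, pooled variance under the null: n = [1.96 √(2 × 0.3 × 0.7) + 0.842 √(0.4 × 0.6 + 0.2 × 0.8)]² / 0.2² = 81.2, so 82 per arm.
- Continuity-corrected: (81.2/4) × [1 + √(1 + 4/(81.2 × 0.2))]² = 90.9, so 91 per arm. This is close to the stated 90.
- Dropout: 90/(1 − 0.28) = 125, close to the stated 126.

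The plan's figure is therefore matched best with continuity correction.

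**4. Power under the present rule and under the fix.** Power = Φ[(d − 1.96 SE₀)/SE₁], where SE₀ is the pooled and SE₁ the unpooled standard error of the difference. With continuity correction, d is reduced by ½(1/n₁ + 1/n₂).

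If three intervention patients are kept and revert to control risk, the intervention rate is (87 × 0.20 + 3 × 0.40)/90 = 20.67%, so the difference falls from 20.0 to 19.33 points.

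For 90 against 90 at 40% and 20%:

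- SE₀ = 0.0683 and SE₁ = 0.0667.
- Uncorrected: (0.2 − 1.96 × 0.0683)/0.0667 = 0.99, giving 83.9%.
- Corrected: d = 0.2 − 0.0111 = 0.1889, and the argument is 0.82, giving 79.5%.

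| Scenario | Uncorrected | Corrected |
|---|---|---|
| 90 v 90, no pregnancy | 83.9% | 79.5% |
| 90 v 87, three intervention patients excluded | 83.3% | 78.7% |
| 90 v 90, three kept at control risk | 81.1% | 76.3% |

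Both scenarios with pregnancies are pessimistic. They take all three from one arm and from the 90 evaluable patients, although that 90 is already net of 28% dropout.

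**The case against.** The strongest reply is that this hardly matters. The assumed count includes zero, the 28% dropout allowance dwarfs any such loss, and the primary comparison barely moves. That stands, and it limits the point to a minor one.

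A second reply is that the rule is a coherent protective choice: pregnancy is already an entry exclusion, the Table 1 targets are not meant for it, and exercise testing is part of follow-up. This justifies stopping those elements, but it does not justify ending observation.

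A third is that so few pregnancies could not inform drug safety and that pregnancy outcome is not a trial outcome. This is true of any summary. It does not remove the value of recording an individual case after study-directed exposure.

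A reader might infer that data already collected are discarded, or that an adverse event already under way goes unrecorded. The protocol says neither, and how such a patient is analysed may be set out in a SAP that is not at hand. A reader might also infer that her clinical care stops. Section D describes the listed assessments, Holter included, as standard AF care, so what ends is their use as trial data.

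Finally, the fix does not gain power. In the assumed worst case it gives less power than exclusion does (81.1% against 83.3% uncorrected, 76.3% against 78.7% corrected). That is the price of following patients as randomised, and it is small.

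**Conclusion.** The point holds as a minor one. The Withdrawal Criteria state a mandatory exit from the whole study and do not separate stopping titration from leaving follow-up. No other section keeps outcome or adverse-event recording going. That data collection ends is the plain meaning of exclusion from the study, although the protocol does not spell it out.

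The gain from changing the rule is confined to individual safety data and to follow-up as randomised. The effect on the primary result is negligible. The count of 0 to 3 pregnancies is an assumption, and the 1.6% of Holters is an extreme bound under it.

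Two stronger readings are not supported. One is that the rule threatens the trial's power or biases its main result: excluding three intervention patients changes power by less than 1 point. The other is that power stays above 80% once the rule is changed. That is so only without continuity correction; with it, power is 79.5% even with no pregnancy.

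**What to change.** Replace the sentence in the Withdrawal Criteria with:

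> If a patient becomes pregnant, study-directed BP titration and any test unsuitable in pregnancy stop; with her consent she stays in scheduled Holter, AFSS and adverse-event follow-up in her randomised group, and the pregnancy outcome is recorded.

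The cost is matching consent wording, a pregnancy-outcome record, and very slight dilution of the treatment difference. In the assumed worst case the loss against no pregnancy is 83.9 − 81.1 = 2.8 points of power uncorrected, or 79.5 − 76.3 = 3.2 points corrected. The sample size need not change.
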